3 STUDY IMPLEMENTATION

3.1 STUDY DESIGN

This is a phase 1/2 single arm study to evaluate the safety and efficacy of baricitinib at doses of 2mg-4mg in patients with cGVHD after SCT. Doses of 0.5mg-20mg have been studied in patients with autoimmune diseases and have demonstrated a good safety profile (Baricitinib Investigator's Brochure, Eli Lilly and Company). Based on studies in patients with RA, there seems to be a plateau efficacy response at doses above 4mg daily, and it is the 4mg daily dose that was taken to the Phase 3 studies. In addition, in anecdotal experience with JAK inhibitors in patients with GVHD, low doses appear to be sufficient for response.

Patients will be enrolled in up to 2 sequential cohorts of up to 21 patients.

The first cohort of patients will be treated with baricitinib starting at a dose of 2mg daily for 12 weeks. For safety purposes, patients who experience a DLT within the first 4 weeks will be able to restart at 1mg daily, and will continue at this dose as tolerated (see Section 3.1.1). If they experience a DLT at this dose, they will be taken off treatment. Regarding efficacy, patients who have a complete response (CR) on 2mg daily at 12 weeks will continue the same dose until the 24 week time point for the primary efficacy endpoint. For patients who have a partial response (PR) or unchanged disease at 12 weeks, the dose will be increased to 4mg daily until the primary efficacy endpoint response assessment at 24 weeks. Following any dose increase to 4mg, patients who experience a DLT within the first 4 weeks will have a dose reduction back to 2mg daily. For patients who experience cGVHD progression at any time within the first 12 weeks on 2mg daily, the dose can be increased to 4mg daily up until the primary efficacy endpoint response assessment at 24 weeks, unless they experience a DLT. Prior to the 12 week response assessment, an initial response assessment will occur at 6 weeks, but there will be no dose changes unless there has been progression or toxicities, as outlined. If at least 1 patient in the first cohort has a PR or CR, the remainder of the study will follow the initial schema as above, and 21 evaluable patients will be treated as part of cohort 1. After the primary response assessment, patients who have unchanged or responding disease will have the option to continue baricitinib for an additional 6 months as tolerated.

[figure not shown]
[figure not shown]
If no patients among the first 7 achieve a CR or PR on 2mg daily at the 12 week response assessment in the first cohort of patients, the second cohort will be enrolled starting at 4mg daily if no safety issues have arisen, with the same parameters for DLT monitoring. Similarly, if 0 of the first 7 treated in cohort 2 have a response, then no further patients will be treated in cohort 2.

If there is at least one patient with a response in the first 7 patients treated on cohort 2, then 21 evaluable patients will be treated in cohort 2.

Concurrent topical and ancillary treatments for cGVHD are allowed per standards of care and will be recorded (see Section 4). Other systemic immune suppression must stay stable or be tapered (systemic immunosuppression taper should be attempted no earlier than after 4 weeks on study), throughout the treatment with baricitinib (with up to 2 steroid pulses allowed for disease stabilization per Section 4.1).

Patients who discontinue therapy for any reason will be followed for up to 24 months after discontinuing baricitinib as indicated in section 3.5.

Peripheral blood samples will be collected prior to treatment, at 2 weeks, at 12 weeks and every 12 weeks thereafter to evaluate cytokine and cellular profiles, STAT phosphorylation, candidate chronic GVHD biomarkers. Pharmacokinetic studies will also be performed at each dose level on day 1 and after 15 days of treatment (Section 5.1.3).

*If ≥ 1 response in cohort 1, 2nd cohort will use identical schema as cohort 1

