Neutrophils $< 1.0 \times 10^9/L$, platelets $< 50 \times 10^9/L$, creatinine ≥ 1.5 times the upper limit of normal **or** estimated creatinine clearance $< 50 \text{ mL/min/1.73m}^2$ (Cockcroft-Gault formula), serum aspartate aminotransferase or alanine aminotransferase concentration $> 3 \times \text{ULN}$ or total bilirubin $\geq 1.5 \times \text{ULN}$

Progressive malignancy, uncontrolled infection or any major organ dysfunction as defined by the protocol

Design:

This is a Phase 1/2 trial to determine the safety and efficacy of baricitinib in patients with cGVHD that is refractory to steroids.

Patients will initially be treated with baricitinib at 2mg daily for 12 weeks. If the response at 12 weeks is a CR and there has not been a DLT, the dose will remain at 2mg daily for an additional 12 weeks, with the primary response assessment at 24 weeks of total treatment. If the response is a PR or stable disease, the dose will be increased to 4mg daily for an additional 12 weeks, with the primary response assessment at 24 weeks of total treatment. If there is progression of disease at any time within the first 12 weeks, the dose can be increased to 4mg daily at that time, and patients will continue for a total of 24 weeks of treatment. Patients will have the option to continue baricitinib for an additional 6 months as tolerated if they have stable or responding disease.

The co-primary endpoint of safety will be determined by rate, severity, and duration of adverse events based on CTCAE v4 criteria. Assessment for DLTs will occur every 2 weeks during the first 4 weeks of each dose level. Safety monitoring will occur every 4 weeks thereafter.

The co-primary endpoint of efficacy will be defined as rate of overall response at 24 weeks per NIH consensus criteria (CR or PR).

Peripheral blood samples will be collected prior to treatment, at 2 weeks, at 12 weeks and every 12 weeks thereafter to evaluate cytokine and cellular profiles, STAT phosphorylation, candidate chronic GVHD biomarkers. Pharmacokinetic studies will also be performed at each dose level.

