2.3.1 Treatment Assignment and Randomization Procedures

Cohorts

Number	Name	Description
1	Phase I cohort	Patients who have undergone hematopoietic allogeneic transplant and have moderate to severe cGVHD that is refractory to treatment with steroids up to 21 patients, for response assessment at 2-4 mg
2	Phase II cohort	Patients who have undergone hematopoietic allogeneic transplant and have moderate to severe cGVHD that is refractory to treatment with steroids after response determination in cohort 1.

Arms

Number	Name	Description
1	Phase I Arm	Baricitinib 2 mg per day, increasing to 4 mg per day in patients who have a partial response or unchanged disease at 12 weeks
2	Phase II Arm	Baricitinib 4 mg per day

Arm Assignment

Patients in Cohort I will be directly assigned to Arm I. Patients in Cohort II will be directly assigned to Arm II.

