3.1.1.1 Dose Escalation

This study will include an intra-patient dose escalation. The starting dose of baricitinib will be 2mg PO daily, a dose that has been well tolerated in previous studies of patients with autoimmune diseases. The first 7 subjects will be treated for a total of 12 weeks at this dose, unless they demonstrate cGVHD progression prior to this, at which time they will increase the dose to 4mg. If patients have a CR, they will continue at this dose until the primary efficacy endpoint. If patients have a PR or unchanged disease (see Section 6.3), the dose will increase to 4mg until the primary efficacy endpoint evaluation takes place at 24 weeks, unless they experience a DLT. If at least 1 patient of the first 7 in cohort 1 has a response, subjects will follow the original dose escalation schema. If 0 of these first 7 patients have a response, then patients will begin to be enrolled onto cohort 2, and will be started at the 4mg PO daily dose initially, unless they experience a DLT, at which time they will decrease the dose to 2mg.

As an early stopping rule for safety, if 2/3 or greater patients at any given dose level experiences a dose limiting toxicity requiring dose reduction or discontinuation, that dose will not be subsequently used.

Intra-patient Dose Escalation Schedule	
Dose Level	Dose of IND Agent
Level -1	1mg
Level 1	2mg
Level 2	4mg

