3.3 DOSE MODIFICATIONS

Patients who develop grade 2 toxicity (not including comorbidities that are present at baseline prior to treatment) for >7 days should hold baricitinib until the toxicity resolves (\leq grade 1) and then restart at the same dose level. Toxicities will be monitored at each study visit. If grade 2 toxicity recurs or worsens, the patient should be reduced to the next lower dose level, unless they are at dose level -1, at which time they should discontinue study drug. Should the toxicity recur

after dose reduction, the patient should be taken off treatment. In the case of multiple simultaneous grade 2 toxicities, these instructions will apply to each individual toxicity separately.

After the 4 week DLT assessment period for any dose level, patients who develop grade 3 non-hematologic or grade 4 hematologic toxicity (not including comorbidities that are present at baseline prior to treatment), or hemoglobin <6.5 g/dL, should hold baricitinib until the toxicity resolves (\leq grade 1 or baseline). If the toxicity resolves within 28 days, patients may restart at the next lower dose level, unless they are at dose level -1, at which time they should discontinue the study drug. Should the toxicity recur at grade 3 non-hematologic or grade 4 hematologic toxicity (not including comorbidities that are present at baseline prior to treatment), or hemoglobin <6.5 g/dL, after dose reduction, the patient should be taken off treatment.

Patients who develop grade 4 non-hematologic toxicity should discontinue and be taken off treatment.

Study drug may be held up to 28 days for resolution of grade 2 or grade 3 toxicity. Otherwise, if no resolution within 28 days, patients will be taken off treatment,

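### Section 3.1 gives two incompatible week-12 instructions for a cohort 1 patient already reduced to 1 mg after a DLT, and the other sections do not settle which applies

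*Combined protocol and SAP*

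**What the plan says.** The week-12 dose decision for cohort 1 is stated in four places.

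- **Section 3.1:** "For patients who have a partial response (PR) or unchanged disease at 12 weeks, the dose will be increased to 4mg daily". The sentence before it covers complete responders and names the dose they must be on: "patients who have a complete response (CR) on 2mg daily at 12 weeks will continue the same dose". The sentence on early progression is likewise limited to patients on 2 mg.
- **Précis, Design:** "If the response is a PR or stable disease, the dose will be increased to 4mg daily for an additional 12 weeks". A no-DLT condition appears only in the complete-response branch: "If the response at 12 weeks is a CR and there has not been a DLT".
- **Section 2.3.1, Arm 1:** starts at 2 mg, "increasing to 4 mg per day in patients who have a partial response or unchanged disease at 12 weeks".
- **Section 3.1.1.1:** restates the increase to 4 mg until the week-24 evaluation, and the sentence closes with "takes place at 24 weeks, unless they experience a DLT".

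Two other provisions can bring a cohort 1 patient down to 1 mg before week 12. Under Section 3.1, a patient with a DLT in the first 4 weeks "will be able to restart at 1mg daily, and will continue at this dose as tolerated". Under Section 3.3, toxicities that are not DLTs can also lead to a reduction; for the more severe ones after the 4-week window, once resolved, "patients may restart at the next lower dose level".

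**The concern.** A patient whose dose was cut to 1 mg for toxicity, and who has PR or unchanged disease at week 12, is covered by the increase rule as worded. If that patient had an early DLT, the same paragraph also says to stay at 1 mg. The two instructions cannot both be followed.

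Three things are at stake. A patient who did not tolerate 2 mg could be moved above it on the wording of the plan. A DLT that followed would be attributed to 4 mg and would feed the stopping rule for that dose and the co-primary safety description. The exposure behind that patient's week-24 response, the co-primary efficacy endpoint, would also depend on which sentence was applied.

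**Working it through.** The plan gives no figure on this point to reproduce. The check is a cross-reading of the dose rules.

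**1. Dose levels** (table in 3.1.1.1): level -1 = 1 mg, level 1 = 2 mg, level 2 = 4 mg.

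**2. The week-12 rule, place by place.**

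| Place | Branch | Limited to patients on 2 mg? | Earlier toxicity addressed? |
|---|---|---|---|
| 3.1 | CR | Yes | No |
| 3.1 | PR or unchanged | No | No |
| 3.1 | Progression before week 12 | Yes | DLT exception, timing unstated |
| Précis | CR | Dose stays at 2 mg | Yes, no DLT |
| Précis | PR or stable | No | No |
| 2.3.1, Arm 1 | PR or unchanged | Arm starts at 2 mg; no limit on current dose | No |
| 3.1.1.1 | PR or unchanged | Context is treatment at 2 mg; no explicit limit | DLT exception, timing unstated |

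**3. Patient A: DLT in weeks 1 to 4 on 2 mg, restarted at 1 mg, PR or unchanged disease at week 12.** The continuation sentence in 3.1 gives 1 mg. The PR/unchanged sentence in 3.1 gives 4 mg. The second is 4 mg / 1 mg = 4 times the first, and two steps up the level table (1 mg to 2 mg to 4 mg), past the level at which the DLT occurred.

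**4. Does 3.1.1.1 settle Patient A?** Its exception has two readings.

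- If it means a DLT at any earlier time, Patient A is exempt from the increase, and 3.1.1.1 disagrees with the literal text of 3.1.
- If it means a DLT after the move to 4 mg, Patient A is not exempt. The cohort 2 sentence in the same section uses the phrase in this sense, for a DLT after starting 4 mg that leads to a reduction to 2 mg.

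The text does not choose between them.

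**5. Patient B: reduced from 2 mg to 1 mg under 3.3 without a DLT.** This can follow recurrent or worsening grade 2 toxicity, or grade 3 non-hematologic or grade 4 hematologic toxicity after the 4-week window that defines a DLT in 3.1.1. No sentence tells this patient to remain at 1 mg, so there is no contradiction. But the 3.1.1.1 exception concerns DLTs only, so neither reading exempts this patient, and 3.3 does not mention the week-12 increase.

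**6. What follows an increase from 1 mg to 4 mg.** Section 3.1.1 counts DLTs within 4 weeks of starting any dose level. The stopping rule in the Précis, 3.1.1.1 and Section 10 acts when two-thirds or more of patients at a dose level have a DLT that requires reduction or discontinuation. Neither provision sets aside patients who had already been reduced, so a qualifying DLT in Patient A or B would count against 4 mg. Section 3.1 would then return the patient to 2 mg, which for Patient A is the level of the first DLT. Section 3.1.1 allows one de-escalation after a DLT and does not say whether that is once per patient.

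**The case against.** The best defence is contextual. Section 3.1 first gives a specific safety rule for patients with a DLT and only then turns to efficacy. The CR and progression sentences are confined to patients on 2 mg, a later DLT sends the patient back to 2 mg as if that were where they came from, and the arm description starts from 2 mg. On that view the increase was written for patients still on 2 mg, and the specific DLT rule governs the general one. This is a plausible account of the intent. It does not remove the conflict: the PR/unchanged sentence lacks the limit its neighbours carry, and no order of precedence is stated.

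The schema figures that accompany 3.1 are not visible in the text available here and may show the branches more clearly. Even so, the prose would still need to agree with them.

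Section 3.3 takes a patient off treatment if toxicity recurs after a reduction. That limits repeated exposure, but it acts after recurrence and does not say whether the week-12 increase should happen.

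Several stronger readings are tempting and are not supported:

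- **That the increase depends on response alone throughout.** Section 3.1.1.1 carries a DLT exception, although an ambiguous one.
- **That the plan instructs a move from 1 mg to 4 mg.** No sentence says so; it is a literal consequence of an unrestricted rule.
- **That different sites would dose the same patient differently.** The study calendar places protocol-driven procedures at one clinical center, with referring physicians only when that is impossible, and Section 7.4.1 describes one research team that discusses each patient weekly.
- **That a number of affected patients can be given.** The documents contain no rate of DLT or of reduction at 2 mg in this population.

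**Conclusion.** The point holds in a limited form. Section 3.1 contradicts itself for a cohort 1 patient restarted at 1 mg after an early DLT who has PR or unchanged disease at week 12. The Précis and Section 2.3.1 repeat the unrestricted increase, and the exception in 3.1.1.1 narrows the problem without resolving it. Patients reduced under 3.3 without a DLT fall into a related gap.

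For one affected patient the discrepancy is 1 mg against 4 mg from week 12 to week 24. Its frequency, and its effect on the two-thirds rule, cannot be sized from the documents. The conclusion assumes only that some cohort 1 patients are reduced before week 12 and remain on treatment with PR or unchanged disease, which the plan's own reduction rules allow for. It merits correction despite the unknown frequency, because it concerns dosing after demonstrated toxicity and touches both co-primary endpoints.

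**What to change.** Reconcile the Précis and Sections 2.3.1, 3.1, 3.1.1, 3.1.1.1 and 3.3 into one consistent statement of what happens at week 12 to a patient already reduced for toxicity, covering separately those who had a DLT and those who did not. State whether the exception in 3.1.1.1 refers to a DLT before the increase, after it, or both. State also, in 3.1.1.1 and Section 10, whether DLTs on 4 mg in previously reduced patients count toward the 4 mg stopping rule. The content of the dosing rule is for the sponsor to decide; no dose or escalation condition is proposed here.

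The cost is a protocol wording amendment with its usual review. It needs no additional patients, visits or tests, and it leaves the sample size unchanged.

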3.1.1 Dose Limiting Toxicity

DLT will be defined as any grade ≥ 3 non-hematologic or grade ≥ 4 hematologic adverse event, or hemoglobin < 6.5 g/dL, within 4 weeks of starting any dose level (1mg, 2mg or 4mg) except those that are clearly and incontrovertibly due to extraneous causes. One inpatient dose de-escalation after a DLT will be permitted in patients who have not experienced cGVHD progression. In patients that have experienced disease progression, further dosing will cease in a patient at the occurrence of the first DLT.

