Occupational therapy evaluation ¹⁵		X									X ¹⁴						X ¹⁴
Skin and Oral Biopsies, saliva collection and oral microbiome swabs ¹⁰	--	X	--	--	--	--	--	--		--	X	--	--	--	--	--	--
TBNK	--	X	X		--		--	X			X	--	X	--	X	X ¹⁶	X ¹⁶
Blood for Immunologic Studies (includes PD) ¹¹	--	X	X	--	--	--	--	X			X	--	X	--	X	X	
Blood for PK Studies ¹²	--	X C1D 1	X C1D 15	--	--		--	--X ¹² C4D1	X	--	--	--	--	--	--	--	--

Assessments ¹	Screen (D -28 to -1)	BL BL / C1 D1	C1 D15	C2 D1	C2 D15	C3 D1	C3 D15	12 weeks C4 D1	C4 D15	C5,6 D1	24 weeks C7 D1	C8,9 D1	36 weeks C10 D1	C11, 12 D1	48 weeks C12 D28	Off Treatment ¹³	Optional 3 month follow up ¹³
Visit Window			±5 days	±5 days	±5 days	±5 days	±5 days	±5 days	+/-5 days	± 7 days	± 7 days	± 7 days	± 7 days	± 7 days	± 7 days	± 7 days	± 7 days
Study drug dispensation/ return/accountability	--	X	--	X		X		X		X	X	X	X	X	X	X	--

- 1 Clinic visits can occur ± 5 days. All procedures at protocol-driven time points are performed at the NIH Clinical Center, but if circumstances make this impossible, these data points will be collected in collaboration with referring physicians.
- 2 Baricitinib at assigned doses for 6 months; another 6-month course of treatment will be allowed for patients with response. Only patients who continue therapy beyond 6 months will be required to have clinical monitoring tests during cycles 7 through 12.
- 3 Use NIH diagnostic criteria for cGVHD ([Appendix B](#) and [Appendix M](#): cGVHD New Patient Data Form). In addition, use [Appendix C](#) for clinical differentiation of acute versus cGVHD.
- 4 Chest CT done at screening; a chest CT may be done at response assessments if clinically indicated; a MRI may be done at baseline if clinically indicated
- 5 Pregnancy tests for females of childbearing potential. A female of childbearing potential (FCBP) is a sexually mature female who: 1) has not undergone a hysterectomy or bilateral oophorectomy; or 2) has not been naturally postmenopausal for at least 24 consecutive months (i.e., has had menses at any time in the preceding 24 consecutive months).
- 6 ECG at indicated intervals screening and as clinically indicated. Prolongation of QTc > 0.5 s or QTc interval increases from baseline > 0.06 s is considered as a safety concern.
- 7 Serologies for HIV, HBV, HCV, CMV PCR, blood and urine cultures, respiratory viral panel, CMV PCR. Cultures with no growth present at 48 hours will be deemed negative. BK virus PCR (urine) will be performed at baseline.

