6.3 RESPONSE CRITERIA

6.3.1 Definitions

Evaluable for toxicity: All patients will be evaluable for toxicity from the time of their first treatment with baricitinib.

Evaluable for efficacy: Patients who complete 6 months of therapy will be evaluable for the primary endpoint of efficacy assessment. Patients who progress earlier will be also included in

the analysis of efficacy. Patients should have received at minimum of 75% of planned baricitinib doses to be evaluable for the primary efficacy 6 month endpoint.

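### The DLT window runs on elapsed time, so a grade 2 hold can use it up and a patient with about 25-32% of the planned doses can count as DLT-free in the two-thirds safety rule

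*Combined protocol and SAP*

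**What the plan says.** - **DLT window.** Section 3.1.1 limits DLTs to qualifying events "within 4 weeks of starting any dose level (1mg, 2mg or 4mg"). The précis uses the same clock: "Assessment for DLTs will occur every 2 weeks during the first 4 weeks of each dose level". So does Section 3.3, which opens its rule for later severe toxicity with "After the 4 week DLT assessment period for any dose level".
- **Grade 2 hold.** Under Section 3.3, patients with grade 2 toxicity "for >7 days should hold baricitinib until the toxicity resolves" and then resume at the same level. Unlike the paragraph that follows it, this rule is not limited to the time after the DLT period. Its maximum length is given separately: "Study drug may be held up to 28 days for resolution of grade 2 or grade 3 toxicity".
- **Stopping rule.** Sections 3.1.1.1 and 10 and the précis stop further use of a dose "if 2/3 or greater patients at any given dose level experiences a dose limiting toxicity requiring dose reduction or discontinuation". They give no minimum exposure, no replacement of patients and no schedule of looks.
- **Evaluability.** Section 6.3.1 says "All patients will be evaluable for toxicity from the time of their first treatment with baricitinib". Its requirement of 75% of planned doses applies to efficacy only.

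**The concern.** Days off drug use up the window. A grade 2 event is not itself a DLT, and resuming the same level is not described as starting a dose level, so no new window opens. Suppose a patient is held in week 2, resumes after week 4 and has a grade 3 non-hematologic event on the 12th dose. Section 3.3 then leads to a hold and a lower level, or to stopping. The event is of the kind the two-thirds rule is meant to count, but it falls outside the definition, and nothing removes the patient from the denominator.

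The bias has one direction: early toxicity that leads to a hold makes the dose look safer. The patients affected are those who have already shown drug-related toxicity. The two-thirds rule is the only numerical study-level safety rule in the plan, and safety is a co-primary objective.

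**Working it through.** The plan gives no operating characteristics for the two-thirds rule, so there is no stated figure to reproduce.

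**Step 1. Smallest exposure inside the window.** Dosing is once daily, so 28 doses are planned in 4 weeks (Section 3.2). Grade 2 toxicity present from Day 1 passes the more-than-7-days trigger at about Day 8 or 9. If the hold is decided only at a clinic visit, the earliest C1D15 visit is Day 15 − 5 = Day 10 (Section 3.7; footnote 1: "Clinic visits can occur ± 5 days").

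| First held day | Doses taken | Share of 28 | Hold length that uses up the window |
|---|---|---|---|
| 8 | 7 | 25% | 21 days |
| 9 | 8 | 29% | 20 days |
| 10 | 9 | 32% | 19 days |

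Each of these holds is shorter than the 28 days allowed.

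**Step 2. One fraction.** Take 7 patients at a level, 4 with a DLT and 1 DLT-free patient held from Day 9 to the end of the window. As written, 4/7 = 57% and the rule is not met. Without that patient, 4/6 = 67% and it is met.

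**Step 3. Probability that the rule is met (illustration).** My assumptions are:

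- a constant DLT hazard per on-drug day, and none while held;
- a true 28-dose risk p = 0.70, just above the two-thirds limit;
- independent patients;
- one look at 6 patients, so 4 DLTs are needed.

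A patient who takes d doses in the window has risk q = 1 − (1 − p)^(d/28).

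- d = 9: q = 1 − 0.3^(9/28) = 0.321
- d = 21 (a 7-day hold): q = 1 − 0.3^(21/28) = 0.595

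Nobody held: P(at least 4 of 6) = 0.324 + 0.303 + 0.118 = 0.744.

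One held with d = 9: P(at least 4 of the other 5) + q × P(exactly 3 of the other 5) = 0.528 + 0.321 × 0.309 = 0.627.

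The other cells follow in the same way:

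| Patients held | 9 of 28 doses | 21 of 28 doses |
|---|---|---|
| 0 | 74% | 74% |
| 1 | 63% | 71% |
| 2 | 49% | 68% |
| 3 | 35% | 64% |

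**Step 4. Effect of the proposed counting.** Under the same assumptions, held patients who resume and complete 28 dosing days carry the full 70% risk again, so the probability returns to 74%. If two held patients never reach the exposure minimum and are left out, 3 of 4 are needed: P = 4 × 0.7³ × 0.3 + 0.7⁴ = 0.412 + 0.240 = 65%, against 49% as written.

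**The case against.** **Size.** The 9-dose column is a worst case: toxicity from the first days, a hold at the earliest visit and no further dose in the window. The documents give neither the frequency nor the length of early holds, and a 7-day hold moves the result by only a few points. The single look at 6 patients is also my assumption. This stands, and the probabilities show direction and possible range only.

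**Observation continues.** A qualifying event during a hold but within 4 weeks is still a DLT. What is lost is exposure, not follow-up, and the zero hazard during a hold somewhat overstates the effect.

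**Other safeguards.** Events after restart are still recorded as adverse events and still lead to action for the individual under Section 3.3. Section 7.4.1 provides for weekly team review of toxicity data, and Section 13.1 allows suspension for unacceptable risk. A reader might infer that such events go unseen or unmanaged, and the documents do not support that. None of these safeguards corrects the two-thirds fraction, however, and none carries a numerical threshold.

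**Denominator.** No section says outright that held patients count as DLT-free. It follows from Section 6.3.1 and the absence of any exclusion or replacement rule. Resuming could also be read as a fresh start of the level, but nothing says so. Where the plan means on-drug time, as for the PK samples in Section 5.1.3, it refers to continuous treatment.

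**Visit windows.** A reader might add that a week-4 visit held a few days late falls outside the window. I do not rely on this. The précis makes that visit a scheduled DLT assessment, so the natural reading is that its findings count.

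**Redefining DLT would reach too far.** Under Section 3.1.1 DLT status also decides whether an individual continues dosing. Moving the definition itself to on-drug time would change who stops treatment. This objection stands and limits the fix to counting.

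**Conclusion.** The gap is real on the text. Followed as written, the two-thirds fraction can include as DLT-free a patient who took about 25-32% of the window's doses, and can miss a qualifying event soon after restart. The direction, toward keeping a toxic dose open, is clear. The size is not: for 1 to 3 held patients out of 6 at a true risk of 70%, the chance of meeting the rule falls from 74% to between 63% and 35% for long early holds, and to between 71% and 64% for 7-day holds. These figures rest on the constant-hazard, single-look model and on an unknown hold frequency. They do not show that the rule will fail in this trial. The passages do not contradict each other; the plan leaves unstated how held days and under-exposed patients count. Because the change is cheap and this is the only numerical study-level safety rule, it is worth making.

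**What to change.** Add a counting rule to Section 10, and repeat it where the two-thirds rule appears in Section 3.1.1.1 and the précis. It should apply to that fraction only:

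1. Count events that meet the Section 3.1.1 severity and causality terms during the first 28 days of dosing at the level. Held days do not use up this period, and an event arising during a hold within it still counts.
2. Include a patient without such an event only if at least 75% of the 28 planned doses (21 doses) were taken. This is the proportion Section 6.3.1 already uses for efficacy.
3. A patient with a qualifying event always counts, whatever the exposure.
4. State that this rule does not alter the DLT definition in Section 3.1.1 or the individual dosing and hold rules in Sections 3.1.1 and 3.3.

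The cost is a few sentences. Some patients enter the fraction later or not at all, so it may rest on slightly fewer patients at a given time.

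### For a cohort 1 patient raised to 4 mg because of cGVHD progression, Section 3.1 and Section 3.1.1 give opposite instructions after a DLT

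*Combined protocol and SAP*

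**What the plan says.** Three parts of the protocol bear on this patient.

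- **Section 3.1 (Study Design), cohort 1.** Patients start at 2 mg. Those with a partial response or unchanged disease at week 12 go up to 4 mg. The text then says: "Following any dose increase to 4mg, patients who experience a DLT within the first 4 weeks will have a dose reduction back to 2mg daily". The next sentence adds a second route to the same dose: "For patients who experience cGVHD progression at any time within the first 12 weeks on 2mg daily, the dose can be increased to 4mg". That sentence ends with a proviso: "the dose can be increased to 4mg daily up until the primary efficacy endpoint response assessment at 24 weeks, unless they experience a DLT". It does not say what to do if the DLT occurs.
- **Section 3.1.1 (Dose Limiting Toxicity).** A DLT is defined within 4 weeks of starting any dose level, 4 mg included. One step down is allowed, but only for some patients: "de-escalation after a DLT will be permitted in patients who have not experienced cGVHD progression". For the rest: "In patients that have experienced disease progression, further dosing will cease in a patient at the occurrence of the first DLT".
- **Section 3.1.1.1 (Dose Escalation).** The first 7 patients stay on 2 mg for 12 weeks "unless they demonstrate cGVHD progression prior to this, at which time they will increase the dose to 4mg". This section gives no DLT action for a cohort 1 patient escalated in that way. Its own reduction to 2 mg is written for cohort 2 patients, who start at 4 mg.

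The Précis also lists progression as a route to 4 mg: "If there is progression of disease at any time within the first 12 weeks, the dose can be increased to 4mg daily at that time".

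**The concern.** Escalation after progression is part of the design. Under Section 3.9.1, cGVHD progression removes a patient from therapy only when a new line of systemic treatment is needed, so patients who have progressed do stay on study drug. If one of them then has a DLT on 4 mg, Section 3.1 continues treatment at 2 mg and Section 3.1.1 ends it.

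At stake is whether a patient whose disease has already worsened stays on a JAK inhibitor after a DLT, in a trial where safety and tolerability is a primary objective. Two such patients could also be handled differently, each in line with some sentence of the protocol.

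**Working it through.** The plan states no figure on this point and no arithmetic applies. The check is to put one patient through each rule.

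**Test case.** A cohort 1 patient progresses on 2 mg at week 6, is raised to 4 mg, and has a grade 3 non-hematologic, non-infectious DLT two weeks later.

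| Source | Does it cover this patient? | Instruction |
|---|---|---|
| 3.1, reduction sentence | Yes: it applies to any increase to 4 mg, and the DLT is within 4 weeks | Continue at 2 mg |
| 3.1, progression sentence | Yes | Proviso about a DLT, but no action named |
| 3.1.1 | Yes: progressed, with a DLT within 4 weeks of starting 4 mg | Stop |
| 3.1.1.1 | Covers the escalation only | No DLT action for this patient |

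The two rules that name an action share the 4-week window and the 4 mg level, and both are directive. They cannot both be followed.

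**Does other text settle it?**

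1. *The DLT proviso in 3.1.* Section 3.1.1.1 uses the same proviso for patients with a partial response or unchanged disease, and 3.1 reduces those patients rather than stopping them. The proviso therefore does not by itself mean stop.
2. *Cross-references.* Section 3.1 points to 3.1.1 where it describes the step from 2 mg to 1 mg. The step from 4 mg to 2 mg carries no such pointer, and no order of precedence is stated.
3. *Section 3.3.* Its hold-and-reduce rule for grade 3 non-hematologic and grade 4 hematologic toxicity applies after the 4-week DLT period. It takes grade 4 non-hematologic toxicity off treatment, so those events are not in dispute. Grade 3 infections have their own restart rule and are set aside here.
4. *Section 3.9.1.* It defines unacceptable toxicity by reference to 3.1.1 and 3.3. This leans toward stopping but leaves the sentence in 3.1 standing.

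**Cohort 2.** The reduction sentence in 3.1.1.1 also lacks a progression exception. The overlap there needs progression and then a DLT, both within the first 4 weeks on 4 mg. The first scheduled response assessment is at week 6, so the progression would have to be found outside the schedule. This is a rare edge case.

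**The case against.** The strongest reply is that the text has a coherent reading. Section 3.1 is the design overview. Section 3.1.1 is the section on DLTs and speaks directly to this patient, and a specific rule normally limits a general one. The order of sentences in 3.1 helps: the reduction sentence follows the partial response and unchanged disease route, while the progression route comes afterwards with its own proviso. If the general sentence prevailed, the stop rule would have little left to do in cohort 1, since the patient escalated for progression is the main person it covers. On this view the protocol lacks a cross-reference and does not contradict itself.

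Most of this stands, and 3.1.1 is the better reading. But it has to be inferred. Section 3.1 speaks of any increase to 4 mg, and a person who follows that sentence literally breaches a safety stop. The weekly team review in Section 7.4.1 and the investigator's discretion in Section 3.9.1 can make handling uniform, but neither says which rule applies. Two figures in Section 3.1 are not shown in the text available and may depict the pathway. They could guide staff but would not make the sentences agree.

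Other mitigating facts also stand. In cohort 1 the 2 mg dose is one the patient has already taken, so it is not a new exposure. With grade 4 non-hematologic events and grade 3 infections excluded, only a subset of DLTs in a subset of patients is affected.

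**Conclusion.** The contradiction holds for cohort 1: Section 3.1 lacks the progression exception that Section 3.1.1 states. Label: wrong as written, minor. The conclusion rests on the wording alone.

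A reader might infer three stronger things that the documents do not support.

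- *That 3.1.1.1 contradicts 3.1.1 to the same degree as 3.1 does.* Its reduction to 2 mg is for cohort 2 patients starting at 4 mg, and the overlap is the edge case described above.
- *That a case is likely.* The documents give neither a progression rate nor a DLT rate. If one assumes that 10% to 40% of cohort 1 is escalated for progression and 10% to 30% of those have a qualifying DLT, the chance per patient is 0.10 × 0.10 = 0.01 to 0.40 × 0.30 = 0.12. The chance of at least one case then runs from 1 − 0.99^7 = 7% (cohort 1 closed at 7, low rates) to 1 − 0.88^21 = 93% (21 patients, high rates). A range that wide, built wholly on assumed rates, shows only that the number is unknown.
- *That the trial's operating characteristics suffer.* The two-thirds safety rule counts a DLT whether it leads to reduction or to discontinuation, so its count does not depend on which section is followed. The sample size does not depend on it either. No effect on power or on the response rate is claimed.

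**What to change.** Add to the 4 mg reduction sentence in Section 3.1: *except in patients who have experienced cGVHD progression, who stop dosing at the first DLT (Section 3.1.1)*. For consistency, add the same exception to the cohort 2 reduction sentence in Section 3.1.1.1. If the sponsor in fact intends these patients to step down to 2 mg, leave those two sentences and amend the de-escalation and stop sentences in 3.1.1 instead.

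The cost is one clause in two sentences, or an edit to one section, made through the usual amendment with IRB review. Sample size, visits and analysis do not change.
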